^a Chronic illness may include, but is not limited to, neurological, cardiopulmonary, gastrointestinal, renal, genitourinary, metabolic, hematologic, auto-immune, or psychiatric disorders or infection.

	
Only if the primary objective is achieved at D42, the 1st secondary objective will be assessed on subjects from the VRVg-2 group for subjects in Primary Series Cohort 1, and this objective will be reached if the observed proportion of subjects with an RVNA titer ≥ 0.5 IU/mL at D42 is higher than or equal to 99% and if the following H_0 hypothesis is rejected:
 
$H_0: P_{VRVg-2} < 97\%$
 
$H_1: P_{VRVg-2} \geq 97\%$
 
This objective will be demonstrated if the overall observed proportion of subjects in VRVg-2 group in Primary Series Cohort 1 with an RVNA titer ≥ 0.5 IU/mL at D42 is at least 99.0%, with the lower limit of the 95% CI of the proportion, calculated using the exact binomial distribution (Clopper Pearson method), is higher than or equal to 97%.
 
• NI testing of 2-dose VRVg-2 versus 2-dose Verorab and Imovax Rabies at D28 
Only if the 1st secondary objective is achieved, and then based on the same approach as the primary objective testing, the 2nd secondary NI objective of VRVg-2 compared to each of the controls will be tested at D28 in each age group in pooled Primary Series Cohort 1 and Cohort 2 subjects.
 
$H_0: P_{VRVg-2} - P_{control} \leq -5\%$
 
$H_1: P_{VRVg-2} - P_{control} > -5\%$
 
With P = proportion of subjects with an RVNA titer ≥ 0.5 IU/mL at D28 (%).
 
The secondary immunogenicity objective of NI at D28 will be demonstrated if each of the non-inferiority between VRVg-2 and both Verorab and Imovax Rabies vaccines is demonstrated for each age group, respectively, in pooled Primary Series Cohort 1 and Cohort 2.
 
• NI testing of 2-dose VRVg-2 at D28 versus 3-dose Imovax Rabies at D42 
Only if the 2nd secondary objective is achieved, then the following NI hypotheses will be tested in each age group (Pediatric subjects: Cohort 1; Adult subjects: pooled Cohort 1 and Cohort 2), respectively:
 
Pediatric subjects (Cohort 1 only):
 
$H_0: P_{VRVg-2} \text{ at D28 (Group 1)} - P_{\text{Imovax Rabies at D42 (Group 3)}} \leq -10\%$
 
$H_1: P_{VRVg-2} \text{ at D28 (Group 1)} - P_{\text{Imovax Rabies at D42 (Group 3)}} > -10\%$
 
Adult subjects (Pooled Cohorts 1 and 2):
 
$H_0: P_{VRVg-2} \text{ at D28 (Groups 1+4)} - P_{\text{Imovax Rabies at D42 (Group 3)}} \leq -10\%$
 
$H_1: P_{VRVg-2} \text{ at D28 (Groups 1+4)} - P_{\text{Imovax Rabies at D42 (Group 3)}} > -10\%$
 
With P_{VRVg-2} at D28 = proportion of subjects with an RVNA titer ≥ 0.5 IU/mL at D28 for VRVg-2 (%), and $P_{\text{Imovax Rabies at D42}}$=proportion of subjects with an RVNA titer ≥ 0.5 IU/mL at D42 for Imovax Rabies (%).
 
NI will be demonstrated for each hypothesis if the lower limit of the 95% CI of the difference of the 2 proportions (P_{VRVg-2} at D28 - $P_{\text{Imovax Rabies at D42}}$) is $> -10\%$, with a similar approach as the primary objective testing.

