--	---

Key Objectives	Age group	Evaluable N in the PPAS	Power (%)
	Primary Objective	Pediatric Subjects (Cohort[C] 1)	VRVg-2: 261 Verorab: 88
			95.4 ^a
			VRVg-2: 261 Imovax Rabies: 88
		Adult Subjects (C1)	VRVg-2: 243 Verorab: 81
			93.8 ^a
			VRVg-2: 243 Imovax Rabies: 81
		Overall: 80.0^a	
	Secondary Objectives		
	#1	Overall (Pooled Pediatric and Adult Subjects in C1)	VRVg-2: 504 86.3^b
#2	Pediatric Subjects (C1)	VRVg-2: 261 Verorab: 88	95.4 ^a
		VRVg-2: 261 Imovax Rabies: 88	95.4 ^a
	Adult Subjects (Pooled C1+C2)	VRVg-2: 570 Verorab: 190	93.8 ^a
		VRVg-2: 570 Imovax Rabies: 190	93.8 ^a
	Overall: 80.1^a		
#3	Pediatric Subjects (C1)	VRVg-2 at D28: 261 Imovax Rabies at D42: 88	>99.9 ^a
	Adult Subjects (D28 from Pooled C1+C2, D42 from C1)	VRVg-2 at D28 (Pooled Cohort 1+ Cohort 2): 570 Imovax Rabies at D42: 81	>99.9 ^a
	Overall: >99.9^a		
#4	Overall (Pooled Pediatric and Adult Subjects in Pooled C1 and C2)	VRVg-2: 831	98.9^b
#5	Overall (Pooled Pediatric and Adult Subjects in C1 only)	Imovax Rabies at D28: 168 Imovax Rabies at D42: 168	90.0^c

a Power calculated using Farrington and Manning (FM) method.

b Power calculated using Binomial Exact method.

c Power calculated using simulation (10000 times, assuming correction coefficient [Rho]=0.5), based on general linear model (GLM) for repeated measured data with categorical response under binomial distribution (link function=identify).

Booster Phase

A subset of 170 adults from Cohort 1 (who received 3-dose PrEP regimen in the primary series) were included in the Booster Phase Cohort 1 at M12, in order to have 102 subjects who received the complete schedule with VRVg-2 vaccine (primary series + booster) in the FASB.

	
A subset of 230 adults from Cohort 2 (who will receive one week 2-dose PrEP regimen in the primary series) will be included in Immunogenicity Persistence and Booster Phase Cohort 2 (including blood samples collection at M6, M12, M18, pre-booster between M24 up to M36, and post-booster between M24 up to M36+D14, and a booster dose between M24 up to M36), in order to have 117 evaluable subjects who received the complete schedule with VRVg-2 vaccine (primary series + booster), assuming approximate 15% of those 230 adult subjects will not be evaluable for booster immunogenicity evaluation at Year 2 up to Year 3 in the FASB.

--	--

Tables of Study Procedures

3-Dose Primary Series – Pediatrics and Adults (Primary Series Cohort 1)

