12.1.2 Hypotheses and Statistical Methods for Secondary Objectives

12.1.2.1 Hypotheses

The secondary hypotheses testing will be considered only if the primary objective is met, and then the secondary objectives will be evaluated sequentially following a fixed-sequence method as specified below (67) (68) (69).

- Superiority in the VRVg-2 group at D42**

Only if the primary objective is achieved at D42, the 1st secondary objective will be assessed on overall subjects from the VRVg-2 group in Primary Series Cohort 1, and this objective will be reached if the observed proportion of subjects with an RVNA titer ≥ 0.5 IU/mL at D42 is higher than or equal to 99% and if the following H_0 hypothesis is rejected.

$$H_0: P_{VRVg-2} < 97\%$$

$$H_1: P_{VRVg-2} \geq 97\%$$

With P = proportion of subjects with an RVNA titer ≥ 0.5 IU/mL at D42 (%).

- NI testing of 2-dose VRVg-2 versus 2-dose Verorab and Imovax Rabies at D28**

Only if the 1st secondary objective is achieved at D42, the 2nd secondary NI objective at D28 will be assessed on each age group of pooled Primary Series Cohort 1 and Cohort 2. The immunogenicity of VRVg-2 will be compared to that of Verorab and Imovax Rabies vaccines at D28, ie, 21 days after the 2nd vaccine injection, using NI testing. For each comparison, the primary parameter will be the difference in the proportion of subjects with an RVNA titer ≥ 0.5 IU/mL at D28 between the 2 compared vaccine groups. The hypotheses tested will be the following:

$$H_0: P_{VRVg-2} - P_{control} \leq -5\%$$

$$H_1: P_{VRVg-2} - P_{control} > -5\%$$

With P = proportion of subjects with an RVNA titer ≥ 0.5 IU/mL at D28 (%).

- NI testing of 2-dose VRVg-2 at D28 versus 3-dose Imovax Rabies at D42**

Only if the 2nd secondary objective is achieved, then the following NI hypotheses will be tested in each age group (Pediatric subjects: Cohort 1; Adult subjects: pooled Cohort 1 and Cohort 2), respectively:

Pediatric subjects (Cohort 1 only):

$$H_0: P_{VRVg-2} \text{ at D28 (Group 1)} - P_{Imovax Rabies} \text{ at D42 (Group 3)} \leq -10\%$$

$H_1: P_{VRVg-2} \text{ at D28 (Group 1)} - P_{Imovax Rabies} \text{ at D42 (Group 3)} > -10\%$

Adult subjects (Cohorts 1 and 2):

$H_0: P_{VRVg-2} \text{ at D28 (Groups 1+4)} - P_{Imovax Rabies} \text{ at D42 (Group 3)} \leq -10\%$

$H_1: P_{VRVg-2} \text{ at D28 (Groups 1+4)} - P_{Imovax Rabies} \text{ at D42 (Group 3)} > -10\%$

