The 2-dose VRVg-2 will be considered as non-inferior to the 2-dose control vaccine if the hypothesis  $H_0$  is rejected.

- **Secondary immunogenicity objective 3: NI testing of 2-dose VRVg-2 at D28 versus 3-dose Imovax Rabies at D42**

Only if the 2nd secondary objective is achieved, the immunogenicity of 2-dose VRVg-2 at D28 will be compared to that of 3-dose Imovax Rabies vaccines at D42, using NI testing in each age group (Pediatric subjects: Cohort 1; Adult subjects: pooled Cohort 1 and Cohort 2), respectively.

For each comparison, the primary parameter will be the difference in the proportions of subjects with an RVNA titer  $\geq 0.5$  IU/mL between the 2 compared vaccine groups.

The following hypotheses will be tested:

Pediatric subjects (Cohort 1 only):

$$H_0: P_{VRVg-2} \text{ at D28 (Group 1)} - P_{Imovax Rabies} \text{ at D42 (Group 3)} \leq -10\%$$

$$H_1: P_{VRVg-2} \text{ at D28 (Group 1)} - P_{Imovax Rabies} \text{ at D42 (Group 3)} > -10\%$$

Adult subjects (Cohorts 1 and 2):

$$H_0: P_{VRVg-2} \text{ at D28 (Groups 1+4)} - P_{Imovax Rabies} \text{ at D42 (Group 3)} \leq -10\%$$

$$H_1: P_{VRVg-2} \text{ at D28 (Groups 1+4)} - P_{Imovax Rabies} \text{ at D42 (Group 3)} > -10\%$$

With  $P_{VRVg-2}$  at D28 is the proportion (%) of subjects with an RVNA titer  $\geq 0.5$  IU/mL at D28 for VRVg-2, and  $P_{Imovax Rabies}$  at D42 is the proportion (%) of subjects with an RVNA titer  $\geq 0.5$  IU/mL at D42 for Imovax Rabies.

The 2-dose VRVg-2 will be considered as non-inferior to 3-dose Imovax Rabies if the hypothesis  $H_0$  is rejected.

In addition, the lower limit of the confidence interval will be assessed against -5% margin as a supplemental NI analysis.

- **Secondary immunogenicity objective 4: Superiority in the 2-dose VRVg-2 group at D28**

Only if the 3rd secondary objective is achieved, then for overall subjects in VRVg-2 group (pooled pediatric and adult subjects) from pooled Cohort 1 and Cohort 2, the 4th secondary objective will be assessed.

The hypotheses tested will be the following:

$$H_{01}: \hat{P}_{VRVg-2 \text{ (Groups 1+4)}} < 99\% \text{ or } H_{02}: P_{VRVg-2 \text{ (Groups 1+4)}} < 97\%$$

$$H_{11}: \hat{P}_{VRVg-2 \text{ (Groups 1+4)}} \geq 99\% \text{ and } H_{12}: P_{VRVg-2 \text{ (Groups 1+4)}} \geq 97\%$$

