Only if the 2nd secondary immunogenicity objective is achieved, based on the similar statistical approach for the primary objective, the non-inferiority of 2-dose VRVg-2 compared to 3-dose Imovax Rabies will be tested, in each age group (ie, in pediatric subjects and adult subjects, respectively), with the two-sided 95% CI of the difference of the 2 proportions, calculated using Wilson score method without continuity correction (2).

The null hypothesis will be rejected if the lower limit of the two-sided 95% CI of the difference of the 2 proportions ( $P_{VRVg-2 \text{ at D28}} - P_{\text{Imovax Rabies at D42}}$ ) is  $> -10\%$ .

The 3rd secondary immunogenicity objective will be demonstrated if all null hypotheses are rejected.

In addition, supplemental analysis will be performed based on NI margin of -5%, using the same statistical method.

- **Secondary immunogenicity objective 4: Superiority in the 2-dose VRVg-2 group at D28**

Only if the 3rd secondary immunogenicity objective is achieved, based on the same statistical approach for the 1st secondary immunogenicity objective, the superiority of VRVg-2 group at D28 will be assessed on overall subjects in VRVg-2 group.

The null hypothesis will be rejected and the 4th secondary immunogenicity objective will be achieved if the observed proportion of subjects with an RVNA titer  $\geq 0.5$  IU/mL at D28 in VRVg-2 group is at least 99%, and the lower limit of the 95% CI of the proportion calculated using the exact binomial distribution (Clopper Pearson method) (1) is at least 97%.

- **Secondary immunogenicity objective 5: NI testing of 2-dose Imovax Rabies at D28 versus 3-dose Imovax Rabies at D42**

Only if the 4th secondary objective is achieved, the 5th secondary immunogenicity objective will be assessed on overall subjects in Imovax Rabies group in Cohort 1 only, using the statistical methods mentioned below, based on NI margin of -10%.

In addition, supplemental analysis will be performed based on NI margin of -5%, using the same statistical method.

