**Table 5.6: Populations used in the analyses**

		Analysis sets	Analysis by	Analysis group
Primary Objective	D42 NI testing	PPAS for D42 (main analysis) FASI, FAS	Randomized vaccine group in the primary series	Cohort 1: • Groups 1, 2, 3
Key Secondary Objectives	Objective 1: D42 Superiority testing in VRVg-2	PPAS for D42 (main analysis) FASI, FAS	Randomized vaccine group in the primary series	Cohort 1: • Group 1
	Objective 2: 2-dose VRVg-2 at D28 versus 2-dose Verorab and Imovax Rabies at D28	PPAS for D28 (main analysis) FASI, FAS	Randomized vaccine group in the primary series	Pooled Cohort 1 and Cohort 2: • Pooled Group 1 + Group 4 • Pooled Group 2 + Group 5 • Pooled Group 3 + Group 6
	Objective 3: 2-dose VRVg-2 at D28 versus 3-dose Imovax Rabies at D42	2-dose VRVg-2: PPAS for D28 (main analysis) 3-dose Verorab/Imovax Rabie: PPAS for D42 (main analysis) FASI, FAS	Randomized vaccine group in the primary series	For Pediatrics, Cohort 1: • Group 1, Group 3  For Adults, pooled Cohort 1 and Cohort 2: • Pooled Group 1+4, Group 3
	Objective 4: D28 Superiority testing in VRVg-2	PPAS for D28 (main analysis) FASI, FAS	Randomized vaccine group in the primary series	Pooled Cohort 1 and Cohort 2: • Pooled Group 1 + Group 4
	Objective 5: 2-dose Imovax Rabies at D28 versus 3-dose Imovax Rabies at D42	2-dose Imovax Rabies: PPAS for D28 (main analysis) 3-dose Imovax Rabies: PPAS for D42 (main analysis) FASI, FAS	Randomized vaccine group in the primary series	Cohort 1: • Group 3
Other Secondary Objectives	Immunogenicity description for primary series	PPAS for D42, PPAS for D28 FASI, FAS	Randomized vaccine group in the primary series	For D0 and D28: Cohort 1 and Cohort 2, respectively; and pooled Cohort 1 and Cohort 2 • Groups 1, 2, 3, 4, 5, 6 • Pooled Group 1 + Group 4 • Pooled Group 2 + Group 5 • Pooled Group 3 + Group 6
	Immunogenicity description for booster phase	FASIB1, FASIB2 FASB1, FASB2 PPAS for booster at M12, PPAS for booster at M24 up to M36	Randomized vaccine group in the primary series	For D42: Cohort 1 • Groups 1, 2, 3

	Immunogenicity Persistence description	FASP FASIP PPAS for booster at M24 up to M36	Randomized vaccine group in the primary series	For M6, M12, M18, and M24 up to M36: Cohort 2 • Groups 4, 5, 6  For booster phase: Cohort 1 and Cohort 2, respectively • Groups 1, 2, 3 • Groups 4, 5, 6

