**Table 5.7: Sample size and power estimation for primary and key secondary immunogenicity objectives**

Key Immunogenicity Objective	Age group	Evaluable N in the PPAS	Estimation/Margin	Power (%)
Primary Objective	Pediatric Subjects (Cohort[C] 1)	VRVg-2: 261 Verorab: 88	Seroconversion (SC) rate at D42: 99.0% NI margin: -5%	95.4 a
		VRVg-2: 261 Imovax Rabies: 88	Same as above	95.4 a
	Adult Subjects (C1)	VRVg-2: 243 Verorab: 81	Same as above	93.8 a
		VRVg-2: 243 Imovax Rabies: 81	Same as above	93.8 a

				Overall: 80.0a
Key Secondary Objectives				
#1	Overall (Pooled Pediatric and Adult Subjects in C1)	VRVg-2: 504	Sufficiency threshold: SC rate at D42 $\geq$ 99.0%, with lower limit (LL) of 95%CI $\geq$ 97.0%	86.3b
#2	Pediatric Subjects (C1)	VRVg-2: 261 Verorab: 88	SC rate at D28: 99.0% NI margin: -5%	95.4 a
		VRVg-2: 261 Imovax Rabies: 88	Same as above	95.4 a
	Adult Subjects (Pooled C1+C2)	VRVg-2: 570 Verorab: 190	SC rate at D28: 96.5% NI margin: -5%	93.8 a
		VRVg-2: 570 Imovax Rabies: 190	Same as above	93.8 a
Overall: 80.1a				
#3	Pediatric Subjects (C1)	VRVg-2 at D28: 261 Imovax Rabies at D42: 88	SC rate at D28: 99.0% SC rate at D42: 99.0% NI margin: -10%	>99.9 a
	Adult Subjects (D28 from Pooled C1+C2, D42 from C1)	VRVg-2 at D28 (Pooled Cohort 1+ Cohort 2): 570 Imovax Rabies at D42: 81	SC rate at D28: 96.5% SC rate at D42: 99.0%NI margin: -10%	>99.9 a
	Overall: >99.9a			
#4	Overall (Pooled Pediatric and Adult Subjects in Pooled C1 and C2)	VRVg-2: 831	Sufficiency threshold: SC rate at D42 $\geq$ 99.0%, with LL of 95%CI $\geq$ 97.0%	98.9b
#5	Overall (Pooled Pediatric and Adult Subjects in C1 only)	Imovax Rabies at D28: 168 Imovax Rabies at D42: 168	SC rate at D28: 96.5% SC rate at D42: 99.0% NI margin: -10%	90.0c

a Power calculated using Farrington and Manning (FM) method.

b Power calculated using Binomial Exact method.

c Power calculated using simulation (10000 times, assuming correction coefficient [Rho]=0.5), based on general linear model (GLM) for repeated measured data with categorical response under binomial distribution (link function=identify).

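### Does the adult test of objective 3 need to be confined to Cohort 1, because most of its VRVg-2 subjects have no 3-dose control randomised alongside them?

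*SAP*

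**What the plan says.** SAP 5.1.2.1 compares two-dose VRVg-2 at D28 with three-dose "Imovax Rabies vaccines at D42, using NI testing in each age group (Pediatric subjects: Cohort 1; Adult subjects: pooled Cohort 1 and Cohort 2"). Protocol 12.1.2.1 opens objective 3 with a gate: "Only if the 2nd secondary objective is achieved, then the following NI hypotheses will be tested in each age group". It then names the samples: "Pediatric subjects: Cohort 1; Adult subjects: pooled Cohort 1 and Cohort 2), respectively". The adult hypotheses in the synopsis, in Protocol 12.1.2.1 and in SAP 5.1.2.1 take VRVg-2 at D28 from Groups 1+4 and Imovax Rabies at D42 from Group 3, with a -10% margin. The synopsis labels them "Adult subjects (Pooled Cohorts 1 and 2").

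The tables agree. The Protocol power tables (synopsis and Table 12.1, row #3) read "Adult Subjects (D28 from Pooled C1+C2, D42 from C1"). SAP Table 5.6 lists "Pooled Group 1+4, Group 3" for adults. SAP Table 5.7 gives "VRVg-2 at D28 (Pooled Cohort 1+ Cohort 2): 570" against 81 for Imovax at D42, with power above 99.9%.

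SAP 5.1.2.2 uses the Wilson score interval for two independent proportions, with no adjustment for cohort or site. It adds that a "supplemental analysis will be performed based on NI margin of -5%, using the same statistical method". SAP 5.1.3.3 plans by-cohort results for adults on the key secondary objectives, including intervals for differences, without hypothesis tests. SAP 5.1.3.1 describes the main immunogenicity results by center.

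**The concern.** Cohort 2 was added by amendment, has its own randomisation list (Protocol 6.7) and runs at one of the four sites (Protocol 5.1.1). It was not to start until COVID-19 confinement measures were lifted (Protocol 1.3.3). Its Imovax arm, Group 6, receives two doses and has no D42 sample. Group 4 therefore enters the adult comparison with no three-dose arm randomised beside it. Objective 2 does not have this feature, since each cohort brings its own controls. The pediatric half of objective 3 and all of objective 5 stay inside Cohort 1.

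If adults in the two cohorts respond differently at D28, about 58% of that difference passes into the adult estimate. A pass at -10%, or at the supplemental -5%, might then reflect who was enrolled in Cohort 2 and not how two doses compare with three. Objective 3 also gates objectives 4 and 5. The fully randomised comparison, Group 1 against Group 3, is planned only as a description.

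**Working it through.** **Inputs.** Cohort 1 adults: 303 VRVg-2 and 101 Imovax. Adult attrition: 21.0% at D28 and 19.8% at D42. Evaluable for the adult test: 570 and 81. Assumed rates: 96.5% at D28 and 99.0% at D42 (SAP 5.5.1 and Table 5.7). The documents give no cohort difference, so every shift below is an assumption.

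**Share from Cohort 2.** Group 1 evaluable: 303 x 0.79 = 239. Group 4: 570 - 239 = 331. Share: 331/570 = 58.1% (planned enrolment: 414/717 = 57.7%).

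**The plan's power.** Farrington-Manning for 570 vs 81, 96.5% vs 99.0%, margin -10%, one-sided 0.025, gives 99.98%, matching the stated >99.9%. A simple check: SE = sqrt(0.965 x 0.035/570 + 0.99 x 0.01/81) = 0.01347; (0.10 - 0.025)/0.01347 - 1.96 = 3.61, so power is about 99.98%.

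**Where bias can come from.** Let a and b be the VRVg-2 D28 rates in Cohorts 1 and 2, and q1 and q2 the three-dose Imovax D42 rates in the same two populations; q2 is unobserved.

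- Contrast with a concurrent control in both cohorts: (0.42a + 0.58b) - (0.42q1 + 0.58q2).
- Contrast the plan estimates: (0.42a + 0.58b) - q1.
- Plan minus ideal: 0.58 x (q2 - q1).

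The VRVg-2 rates cancel. Only a cohort difference in the three-dose control matters, and q2 cannot exceed 100%:

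- q1 = 99%: bias towards VRVg-2 is at most 0.58 x 1 = 0.58 points.
- q1 = 97%: at most 0.58 x 3 = 1.7 points.
- q2 below q1: the bias runs against VRVg-2.

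**The worrying scenarios.** Put Cohort 1 at a margin, raise the Cohort 2 VRVg-2 rate, and hold Group 3 at 99%. The worst case sets q2 = 100%, so pooled Imovax is 99.58%. The pass rates enumerate the Wilson rule with objective 3 taken alone.

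| Margin | Cohort 1 / Cohort 2 VRVg-2 | Pooled VRVg-2 | Difference vs 99% | Worst case vs 99.58% | Pooled rule passes | Cohort 1 rule passes |
|---|---|---|---|---|---|---|
| -10% | 89% / 91% | 90.16% | -8.8 | -9.4 | 13.8% | 3.0% |
| -10% | 89% / 93% | 91.32% | -7.7 | -8.3 | 37.2% | 3.0% |
| -5% | 94% / 96% | 95.16% | -3.8 | -4.4 | 19.2% | 3.2% |
| -5% | 94% / 98% | 96.32% | -2.7 | -3.3 | 57.2% | 3.2% |

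In every row the pooled adults are inside the margin, even against the least favourable concurrent control. These passes are correct decisions about the population that the hypothesis names. With a shift of -2 points from 89%, the pooled rule is the stricter one: 0.7% against 3.0%.

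A true error needs the control to differ. If both cohorts are at 89% for VRVg-2 and q2 = 100%, the ideal contrast is 89 - 99.58 = -10.6. The pooled rule then passes 3.6% of the time, against 3.0% for the Cohort 1 rule.

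**The gate.** Adult objective 2 must pass first. With controls at the planned 96.5% at D28 and Cohort 1 VRVg-2 at 89%, the joint chance of passing both adult objectives is under 0.01% for a shift of +2 or +4.

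**Price of confining the test to Cohort 1** (239 vs 81, margin -10%, Imovax 99% at D42, Wilson rule):

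| Adult D28 rate | Pooled power | Cohort 1 power |
|---|---|---|
| 96.5% | >99.9% | 98.9% (98.3% by Farrington-Manning) |
| 95.0% | 99.7% | 88.0% |
| 93.9% | 95.6% | 68.9% |

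The last rate is the adult Imovax result at D21 in the sponsor's study cited in Protocol 5.4.1. At the supplemental -5% margin and 96.5%, power is about 64% pooled and 35% in Cohort 1.

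**The case for a change.** The best case for changing the test is that randomisation should support a confirmatory claim whenever it can, and here it can: at the planning rates Cohort 1 alone keeps more than 98% power. A cohort difference is also plausible. Protocol 5.4.1 says variable response is particularly relevant in adults and that those over 65 tend to respond late or low. Adults form a single age stratum in the randomisation (Protocol 6.7), and three of the four sites are absent from Cohort 2. The planned by-cohort comparison would reveal only a fairly large shift: at 96.5% the 95% half-width for VRVg-2, 239 against 331, is about 3.1 points. If the intended claim concerned Cohort 1 adults alone, the pass rates in the working would be genuine errors.

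Some of this stands. The adult contrast is partly non-randomised, and a reader should be told so. What does not stand is the step from a higher D28 rate in Cohort 2 to a biased conclusion. The hypothesis is written for pooled adults, consistently in both documents, and nothing in them makes Cohort 1 the target population. By D28 both cohorts have had the same two doses on the same schedule, and the assay and blinded laboratory are shared. The -5% look, where the pass rates are highest, is supplemental and does not decide objective 3.

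**Conclusion.** No change to the plan follows. The pooled adult comparison is openly stated, its power reproduces, and it is a fair trade-off: it uses all adults who contribute a two-dose response, at the price of a control that is concurrent for only about 42% of them. At a three-dose Imovax rate of 99%, that price is at most about 0.6 points in favour of VRVg-2, or about 1.7 points at 97%, against a 10-point margin. A lower control rate in Cohort 2 would count against VRVg-2. Replacing the confirmatory test would take 58% of the adult VRVg-2 sample out of it and would cost between 1 and 27 points of power across D28 rates from 96.5% to 93.9%.

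The conclusion rests on two assumptions: that the target is the pooled adult population, as the hypotheses state, and that Imovax at D42 is close to its planned rate. The bound loosens as that rate falls. The Group 1 versus Group 3 interval planned in SAP 5.1.3.3 can be shown beside the pooled result, with a statement that the adult conclusion rests partly on a non-randomised comparison. That is interpretation in the report, not an amendment.
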